- **Value Difference Modulated by Value Mean (F12).** Factor F12 will assess the interaction between value difference (F1) and value mean (F2). F12 is an indicator of value learning bias, corresponding to the classic Probabilistic Selection Task (PST)

“choose A vs. avoid B” measure (assessing whether participants perform better either at choosing the most rewarding stimuli or at avoiding the least rewarding stimuli, when each of these are paired with neutral stimuli).

- **Block Size Mean (F3)** is the mean of the sizes of the blocks the two stimuli originated from in the learning phase. For example, if one stimulus (image) in a pair stems from a block of size 2 and the other stimulus stems from a block of size 4, the set size mean is 3. Possible values are from 2 to 5 in steps of 0.5.
- **Value Difference Modulated by Block Size Mean (F13)**. Factor F13 will assess the interaction between value difference (F1) and block size mean (F3). High values for block size mean (e.g., 5 or 6) imply that both stimuli in a pair are from rather large blocks (e.g., of sizes 5 or 6). In such cases the effect of value difference may be less pronounced compared to what might be observed if both stimuli in a pair are from smaller blocks. Smaller block sizes might enable more robust learning leading to a more pronounced effect of value difference for smaller compared to large block size means. Alternatively, larger block sizes might require more use of RL over WM and thus lead to a more pronounced effect of value difference.
- **Block Size Difference (F4)** is the difference in the sizes of the blocks the two stimuli originated from in the LP. For example, if one stimulus in a pair stems from a block of size 2 and the other image stems from a block of size 4, the block size difference is 2. Block size differences will also be calculated as ‘block size right stimulus originated from’ minus ‘block size left stimulus originated from’; hence results can range from -4 to 4 in steps of 1.
- **Learning Block Difference (F5)**. 13 blocks are used in the LP. If e.g. the left image was learned in the 2nd block and the right image in the 6th block, the learning block difference will be 4 (=6-2). Differences will be derived as ‘right’ minus ‘left’. Values can thus range from -12 to 12 in steps of 1.
- **Previous Trial Choice (F6)**. The factor is coded as ‘L’ or ‘R’ and indicates the side of the previously chosen stimulus. Significant effects on this factor may be interpreted as an increase in choice stickiness, and thus possibly a decrease in involvement in the task.

For each pair of stimuli, denote by  $z$  the binary response taking values 1 (if the participant chose the right stimulus in the pair) and 0 (if the participant chose the left stimulus in a pair).

Logistic regression analysis modelling the likelihood the participant **chooses the right stimulus of a pair (variable z)** will be performed for each session with model

$$\log(p/(1-p)) = \beta_0 + \beta_1 \cdot F1 + \beta_{12} \cdot F12 + \beta_{13} \cdot F13 + \beta_4 \cdot F4 + \beta_5 \cdot F5 + \beta_6 \cdot F6 + \varepsilon.$$

Factor F2 will not be included because there is no reason to believe why value mean should be systematically associated with the likelihood to choose the right stimulus of the pair. Only the three parameters  $\beta_0$ ,  $\beta_1$ , and  $\beta_{12}$  are of primary interest. The other factors have been added to the model to improve the model fit but (even if significant) are not of scientific interest. Any records where any of the six covariates is missing or where information on the side chosen is not available will be excluded from analysis. Based on the resulting data set,

- a) Each variable of F1 to F6 will be standardized within each participant and visit by subtracting the within participant and visit mean and dividing by the within participant and visit standard deviation.
- b) The two interaction terms F12 and F13 will then be derived as the product of the corresponding standardized variables F1 and F2 as well as F1 and F3.
- c) Subsequently, the two interaction terms F12 and F13 will again be standardized using the same approach as described in a).

The regression coefficients will allow the following interpretation:

**Factor F1 (Value Difference):** Positive values for  $\beta_1$  will mean that the likelihood to choose the right side will increase with the (right minus left) value difference F1. Positive value differences imply that the right side is the correct choice; hence positive values for  $\beta_1$  imply increasing likelihood to make a correct choice with increasing difference between stimuli.

**F1 and F2 (Value Mean) Interaction (F12, Value Difference modulated by Value Mean):** Effect of F1 (value difference) on  $p$  depends on the level of F2 (value mean): F2 being close to 0 or close to 2 imply that there can only be very small value differences in such pairs whereas F2 being close to 1 allows F1 (right minus left) to range from -2 to 2. Hence, a positive association between  $p$  is expected for F2 around 1 but less so for F2 close to 0 or 2 and should manifest itself in the  $\beta_{12}$  interaction term associated with F12. Positive values of  $\beta_{12}$  are associated with "choose A (choose one with better reward)" being improved over "avoid B (avoid one with less reward)", while negative values would correspond to "choose A" being worse than "avoid B". An increase in  $\beta_{12}$  is expected for an effective treatment.

**F1 and F3 (Block Size Mean) Interaction (F13):** Like F12 smaller block size means are expected to lead to a stronger association of value difference (F1) with the likelihood to choose the right stimulus.

Note that main effects for F2 and F3 are not included. The value mean (F2) of a pair should not impact the likelihood to choose R or L. Same applies to F3, which also as such is not expected to have an effect.

**Factor F4 (Block Size Difference):** Significant effects of F4 (i.e., positive coefficients for  $\beta_4$ ) could be interpreted as a change in effort avoidance, as it indicates a tendency to prefer those stimuli encountered from easier blocks independently of learned value. In other words, F4 measures to what extent the choice of the participant is driven by block size beyond value they have gained.

**Factor F5 (Learning Block Difference):** i) In case a participant would always correctly choose the higher value stimulus and ii) assuming the higher value stimulus is equally often on the right or left side, the coefficient  $\beta_5$  associated with factor F5 in the model above is expected to zero. Hence, significant effect of F5 could be interpreted as a change in long term memory use, as it indicates a tendency to be sensitive to recency. F5 is intended to capture effects on learning that are independent of objective value. Decision making literature shows that many other factors may influence choice, beyond strict economic preference. A preference based on how recently the stimulus was seen is a possible factor, which F5 is attempting to capture.

The analysis will focus on the evaluation of the coefficient  $\beta_{12}$  associated with the interaction 'value difference modulated by value mean' in the model above. This is considered to capture the "choose A/avoid B" paradigm. Model

$$Y_{ijk} = \mu + \tau_i + \pi_j + \varepsilon_{ijk},$$

where  $\mu$  is the general mean,  $\tau_i$  are the effects of treatment,  $\pi_j$  are the effects of visit, and  $\varepsilon_{ijk}$  are random errors assumed to be correlated across visits within each participant, i.e.,  $\text{Cov}(\varepsilon_{i1k}, \varepsilon_{i2k}) = \text{Cov}(\varepsilon_{i2k}, \varepsilon_{i3k}) = \sigma_1$  and  $\text{Cov}(\varepsilon_{i1k}, \varepsilon_{i3k}) = \sigma_2$  and  $\text{Var}(\varepsilon_{ijk}) = \sigma^2$ , will be applied to the coefficients  $\beta_{12}$ . Results will be reported as least squares means by treatment arm as well as differences between treatment arms together with 90% confidence intervals.

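### The RLWM test phase compares arms on beta12 only, and beta12 cannot tell better choose-A learning from a selective loss of avoid-B learning, or detect a uniform change in value learning

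*SAP*

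**What the plan says.** SAP 4.5.3.2, under Statistical Analyses, models the probability of choosing the right-hand stimulus of each pair. F1 is the value difference within the pair, F2 is the mean value of the pair, and F12 is their interaction.

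- The SAP labels F1 as its indicator of reinforcement-learning value learning. Positive beta1 values "imply increasing likelihood to make a correct choice with increasing difference between stimuli".
- On the interaction it says: "F12 is an indicator of value learning bias". A positive beta12 is described as choosing the better-rewarded stimulus being stronger than avoiding the less-rewarded one, which is a relative statement. A rise in beta12 "is expected for an effective treatment".
- On which coefficients matter, the SAP singles out three, namely beta0, beta1 and beta12. It says that they "are of primary interest. The other factors have been added to the model to improve the model fit".
- On the arm comparison: "The analysis will focus on the evaluation of the coefficient" beta12. A model with treatment and visit effects is applied to the beta12 values. "Results will be reported as least squares means by treatment arm as well as differences between treatment arms together with 90% confidence intervals".

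No between-arm result is specified for beta1, or for choose-A and avoid-B performance taken separately. The other RLWM output by arm is the learning-phase percentage of correct choices in late trials and large blocks. The exploratory endpoint for the test phase, in Protocol Section 3 and SAP 2.2, is the interaction.

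**The concern.** A contrast rises when its first part goes up or when its second part goes down. Beta12 measures how much steeper the effect of value difference is in high-value pairs (choose A) than in low-value pairs (avoid B). Two opposite changes in the patient can therefore give the same rise, and the SAP attaches its expected direction to a rise without separating them. Beta1 moves in opposite directions in the two cases. The SAP estimates it in every session and names it as of primary interest, but gives no result for it by arm.

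The second gap follows from the first. If both slopes improve or both worsen by the same amount, the contrast stays near zero, so a uniform change in value learning does not show.

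The stated objective is the drug's effect on reward learning. What is at stake is whether the test phase can be read as information on that objective.

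**Working it through.** **No planned figure to reproduce.** The documents give no expected value, SD or power for beta12.

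**Algebra.** Let f1 and f2 be F1 and F2 standardized within participant and visit, and let s be the SD of the product f1 × f2. The SAP standardizes that product again, so F12 = (f1 × f2 − mean)/s. At the average block-size mean, the log-odds slope per SD of value difference is

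slope(f2) = beta1 + beta12 × f2 / s.

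At one SD above and below the mean of F2:

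- high-value slope = beta1 + beta12/s
- low-value slope = beta1 − beta12/s
- therefore beta12 = s × (high − low)/2 and beta1 = (high + low)/2.

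Raising the high slope by d and lowering the low slope by d both add s × d/2 to beta12. Beta1 goes up by d/2 in the first case and down by d/2 in the second. If both slopes move by d, beta12 does not change.

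**Simulation of the SAP model.**

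- From the SAP: 36 stimuli in 10 blocks, 10 presentations each, reward probabilities 0.25, 0.50 and 0.75, up to 156 pairs per session, and F1 to F6, F12 and F13 standardized as specified.
- Assumed: mean learning accuracy 80%; pairs drawn at random; a reference slope of 2 per point of value difference in both halves of F2, shifted by 1 per scenario; 1500 sessions per scenario.
- The Monte Carlo standard error of mean beta12 is about 0.006 to 0.008. The mean of s was 0.92 to 0.93. The two slopes were computed session by session and averaged.

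| Scenario | beta1 | beta12 | Accuracy | High-value slope | Low-value slope |
|---|---|---|---|---|---|
| Reference | 1.12 | -0.02 | 69.5% | 1.10 | 1.14 |
| Choose A better | 1.39 | +0.19 | 72.7% | 1.60 | 1.18 |
| Avoid B worse | 0.84 | +0.21 | 65.2% | 1.07 | 0.61 |
| Both better | 1.70 | -0.01 | 75.8% | 1.70 | 1.71 |
| Both worse | 0.56 | -0.01 | 60.8% | 0.56 | 0.57 |

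- A choose-A gain adds 0.189 + 0.018 = 0.21 to beta12. An avoid-B loss adds 0.206 + 0.018 = 0.22. The corresponding changes in beta1 are 1.39 − 1.12 = +0.27 and 0.84 − 1.12 = −0.28.
- A true gain confined to avoid B lowers beta12 to -0.24, although accuracy rises to 72.8%.
- Uniform changes leave beta12 at -0.01 while accuracy ranges from 60.8% to 75.8%.
- Beta1 and the two slopes separate all five rows.

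**Learning-phase output.** It counts correct button presses. Reward size is outside the participant's control, and the SAP says the learned reward values are assessed in the test phase. The learning-phase percentage therefore does not show which half of the beta12 contrast has moved.

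**The case against.** The strongest case for the plan is that beta12 is the declared endpoint and is openly called a bias measure. The protocol and SAP link the difference between choosing and avoiding to striatal dopaminergic measures. A bias index that stays flat when both sides improve is doing its job. This stands, and it is why beta12 should remain the endpoint. It does not explain why beta1, named as of primary interest, has no result by arm.

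Two stronger readings are tempting, and the documents do not support either.

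- A reader might infer that any drug that impairs value learning would look effective. That holds for impairment concentrated in low-value pairs. It can also hold for uniform impairment where beta12 is already negative: in the simulation, halving both slopes from such a start moved beta12 from -0.35 to -0.18. Uniform impairment from no bias leaves beta12 near zero, so it would be missed, not read as benefit.
- A reader might infer that the SAP treats a rise in beta12 as proof of efficacy. It says only that an effective treatment is expected to produce a rise. It sets no RLWM success threshold or decision rule.

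The stakes are also small. The endpoint is exploratory, SAP Section 1 reports 27 patients randomized, and SAP Section 4 rules out formal tests. In the reference scenario the session SD of beta12 was 0.26. With an assumed 13 and 14 patients, sampling noise alone gives a single-visit 90% half-width of about 1.71 × 0.26 × √(1/13 + 1/14) = 0.17, close to the simulated shift. SAP 4.5 also says that no statistical modelling will be done, which leaves unclear whether this model will be run at all.

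Finally, the simulated sizes rest on inputs the SAP does not give. The SAP is also not consistent on the task layout: 36 stimuli in 10 blocks in one place, but 49 stimuli and 13 blocks in others. It selects pairs from each participant's own responses, not at random. This affects the sizes. The direction follows from the definition of beta12.

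**Conclusion.** The point holds in limited form. With an arm comparison on beta12 only, the test phase cannot tell better choose-A learning from a selective loss of avoid-B learning, and it misses a uniform change in value learning. Under the assumptions above, the two opposite cases shift beta12 by +0.21 and +0.22 and beta1 by +0.27 and −0.28.

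The risk is a misread exploratory signal, not a false confirmatory claim, and no decision in the documents is shown to depend on it. Part B has its own analysis document, which is not available here, so this conclusion covers the Part A plan only. The change is worth making because the missing coefficient is already estimated and settles the ambiguity.

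**What to change.** 1. In the closing paragraph of the RLWM Statistical Analyses (SAP 4.5.3.2), keep beta12 as the endpoint. Apply the same treatment and visit model to beta1 and to the value-difference slopes at one SD above and below the mean of F2, computed per session as beta1 ± beta12/s. Report least squares means, arm differences and 90% confidence intervals for each. Dividing by s is needed because F12 is standardized a second time; plain beta1 ± beta12 would understate the gap between the slopes by about 7% to 8% at s = 0.92 to 0.93.

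2. In the paragraph interpreting the F1 and F2 interaction, add a note that a rise in beta12 is to be read together with beta1 and the two slopes, and is not by itself evidence of improved reward learning. This should be an interpretation note, not a new success criterion.

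3. State in SAP 4.5 that the RLWM models are an exception to the rule of no modelling, if they are to be run.

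The cost is SAP wording and three more exploratory rows from fits already made, with no new data. The downside is three more estimates in a small sample, each to be read descriptively.

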#### **4.5.3.3 Brief Assessment of Cognition in Schizophrenia (BACS)**

To explore the effects of RO6889450 on overall functioning/cognition, the Brief Assessment of Cognition in Schizophrenia (BACS) is employed.

The BACS is designed to measure cognition in schizophrenia. The domains of cognitive function measured by the BACS include:

- verbal memory (measure: number of items recalled total, range: 0–75, ZDSCAT=VERBAL MEMORY; VERBAL MEMORY TSCORE),
- working memory (measure: digit sequencing, number of correct sequences, range: 0–28, ZDSCAT=DIGIT SEQUENCING; DIGIT SEQUENCING TSCORE),
- motor speed (measures: the number of tokens correctly placed into the container, range: 0–xx, ZDSCAT=TOKEN MOTOR TASK; TOKEN MOTOR TASK TSCORE),

- attention and speed of processing (measure: symSbol coding - number of correct numerals, range: 0–110, ZDSCAT=SYMBOL CODING; SYMBOL CODING TSCORE),
- executive functions (measure: tower of london, number of correct responses, range: 0–22, ZDSCAT=TOWER OF LONDON; TOWER OF LONDON TSCORE), and
- verbal fluency (measure: number of words generated = verbal fluency total, range: 0-xx, ZDSCAT=VERBAL FLUENCY; VERBAL FLUENCY TSCORE)

The BACS domains found to be impaired in schizophrenia. The BACS is found to be a valid outcome measure for the effects of medication, and therapy on cognitive function, and is an indicator of functional relevance with respect to independent living skills, performance-based assessments of everyday living skills, and interview-based assessments of cognition in participants with schizophrenia. The BACS is administered by qualified site raters using the tablet-based BACS App.

In study **Part A**, the assessments for BACS are performed at Day 1 (baseline), Day 42, and Day 84/EOT. All assessments will be assigned to analysis study days according to the following table:

Assessment Day	Assigned Study Day
>88 or >4 days after last study medication	FU, will not be included in statistical analysis
64-88	84
2-63	42
-2-1	1
<-2	-35, will not be included in statistical analysis

In general, if at least one item score is missing or not ratable, the total/factor/subscale scores that include the item will be set to missing.

The BACS measure from each of the 6 test (number of items recalled total, number of correct sequences, number of tokens correctly placed, cat) will be provided by absolute values and standardized t-scores (verbal memory, digit sequencing, token motor, verbal fluency, symbol coding, tower of London, BACS composite score) will be provided.

BACS t-scores and change from baseline in t-scores will be summarized by assessment visit.

#### **4.5.3.4 Virtual Reality Functional Capacity Assessment Tool (VRFCAT)**

To explore the effects of RO6889450 on overall functioning/cognition, the Virtual Reality Functional Capacity Assessment Tool (VRFCAT) is employed.

The VRFCAT is a computerized measure of functional capacity, with the potential to demonstrate real-world functional improvements associated with cognitive change. It presents participants with a realistic simulated environment to recreate routine activities

**RO6889450—F. Hoffmann-La Roche Ltd**

**25/Technical Document for Statistical Analysis BP40283 PART A**

of daily living (Ruse et al 2014). It consists of four mini-scenarios that follow a story, including: (1) exploring a kitchen, (2) catching a bus to a grocery store, (3) finding/purchasing food in a grocery store, and (4) returning home on a bus.

In study **Part A**, the assessments for VRFCAT are performed at Day 1 (baseline), Day 42, and Day 84/EOT. All assessments will be assigned to analysis study days according to the following table:

Assessment Day	Assigned Study Day
>88 or >4 days after last study medication	FU, will not be included in statistical analysis
64-88	84
2-63	42
-2-1	1
<-2	-35, will not be included in statistical analysis

VRFCAT adjusted total time, errors and forced progressions t-scores and change from baseline in t-scores will be summarized.

#### **4.5.3.5 Smoking Dependence**

To explore the effects of RO6889450 on changes in smoking dependence Fagerstrom Test for Nicotine Dependence (FTND) total score is employed.

The Fagerstrom Tolerance Scale is used to assess nicotine consumption during the study. The Fagerstrom test is a standard instrument for assessing the intensity of physical addiction to nicotine providing an ordinal measure of nicotine dependence related to cigarette smoking. It contains six items that evaluate the quantity of cigarette consumption, the compulsion to use, and dependence. Yes/No items are scored from 0 to 1 and multiple choices are scored from 0 to 3. The items are summed to yield a total score of 0 to 10, see [Appendix 8](#)). The higher the total Fagerstrom score, the more intense is the participant's physical dependence on nicotine.

In study **Part A**, FTND is assessed at Day 1 (baseline), Day 42, Day 84/EOT and Day 112 (FU)..

In general, if at least one item score is missing or not ratable, the total/factor/subscale scores that include the item will be set to missing.

The FTND total score and the change from baseline in total score will be summarized by assessment visit.

#### **4.5.3.6 Levels and Patterns of Social and General Activity (optional)**

'Phone Usage Monitoring' will be carried out as an exploratory and optional tool to help understand a potential therapeutic effect of RO6889450, regarding participant's functioning and behavior and to refine such outcome measures for future studies.

Participants who have a personal Android-based smartphone will be asked to download a Phone Usage Monitoring App. Through the Smartphone App the phone usage of the participants will be monitored and evaluated, from which levels and patterns of social and general activity of the participants can be inferred. The App will record:

- **Time spent on the phone and on different Apps:** the power state of the phone (screen on/off, power connected/disconnected, and shutdown/restart/boot) and all screen touch events will be recorded. Given the wide variety of apps, each app is grouped into one of the three broad categories: social, engagement, and entertainment. Every 15 mins the total number of apps that belong to each of these three categories will be computed from the process stack. Then the increases in the number of apps for each of categories will be computed.
- **Number and timing of phone calls, and their duration:** the number and duration of incoming and outgoing calls per day will be recorded
- **Number and timing of messages:** the number of incoming and outgoing text messages per day will be recorded
- **Number of contacts and level of interaction with contacts**
- **Ambient noise:** the mean audio amplitude will be computed to determine the acoustic conditions ranging from quiet to loud environments. Also the standard deviation of the audio amplitude will be computed to gauge if the audio environment is ambient (e.g., loud air conditioning) or active (e.g., people talking).
- **Location:** the GPS chip will be used to record the spatial location of the phone over time. Total distance traveled, maximum displacement from the home, standard deviation of distances, location entropy, and duration of time spent at primary location and at secondary location will be recorded on a daily basis. A locational routine index over a period of time will be computed to quantify the degree of repetition in terms of places visited. The number of new locations visited in a day that have not been seen previously can be also monitored. Sampled location readings/coordinates will be clustered into primary, secondary or other location over the entirety of a participant's data. The first and second largest clusters are labeled as the primary and secondary locations, respectively.

Collected data will be immediately encrypted and buffered on the device until a Wi-Fi connection becomes available, at which point the data are uploaded to a database on the study server. The data can be analyzed using an evolving suite of software.

The decision to install the App is optional but encouraged. Participants can at any time point decide to remove the App from the smartphone.

The phone usage is continuously monitored from the placebo compliance period up to end of the follow-up, i.e., continuously from Week -2 to Day 112 (FU)

